7.1 Aims and objectives

To evaluate the diagnostic accuracy for the 2 commercially available combined HR-POCT platforms (MeMed BV and FebriDx) and for the Triverity test, for the diagnosis of bacterial and viral infection, against the reference standard of clinical adjudication.

Outcome measures

Key outcome measures:

Positive percentage agreement (PPA) negative percentage agreement (NPA), Positive Predictive Value (PPV), Negative Predictive Value (NPV), Overall accuracy, AUROC, all with 95% confidence intervals.

Exploratory outcome measures:

To evaluate the equivalence of EDTA blood and PAXgene RNA blood on gene expression values for the prototype Cepheid HR test (Xpert Bacterial vs. Viral assay).

Study design and methods

We will conduct a fully powered diagnostic accuracy study performed on samples prospectively collected from adults presenting with ARI (7) using the Southampton Research Biorepository (SRB) and including routinely collected clinical data including results of diagnostic testing for viruses and bacteria in addition to baseline clinical, laboratory and radiological data, and outcome data. The reference standard used by regulators for defining bacterial and viral infection is clinician adjudication (as no sufficiently accurate gold standard test exists) which take account of detailed clinical data including diagnostic tests for pathogens, blood test results (eg white cell count, PCT) radiological tests, and other data (37).

In accordance with guidelines, adjudication will be performed independently by three blinded experts, with a system for arbitration where there is discordance (37). Full methods for clinical adjudication are detailed in Tanner A, at al, Journal of Infection 2024 (38) Measures of diagnostic accuracy will be calculated for each HR test separately and compared.

Trial overview for patient-participants

Adult patients with acute respiratory illness in Southampton General Hospital's Emergency Department (ED) and Acute Medical unit (AMU) will be identified and assessed for eligibility for the trial. Potential participants would have been seen and assessed by the triage nurse or other triaging clinician but may not have been fully treated by their clinician. The triage nurse or other triage clinician may highlight potential participants to the study team. Potential participants will receive a participant information sheet, and be invited to ask questions, as part of the informed written consent process.

Once SRB generic consent has been obtained participants will be asked for 2 combined nose and throat swabs (1 sent for immediate respiratory viruses testing and the other to be stored at -80°C), finger-prick capillary blood sampling (for immediate FebriDx testing) and venous blood sampling (for ETDA, serum and RNA PAXgene tubes). Results of the FebriDx test will not be shared with treating clinicians or patients. The other tests will be performed retrospectively on stored samples at least 30 days later and will not influence clinic care.

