Title	Comparison of the performance of 3 Host Immune response tests for distinguishing bacterial and viral acute respiratory infection (CHIRP study).		
Short Title	Performance of 3 host response tests		
Design	Observational, retrospective, diagnostic accuracy study		
Participants	Adults ≥ 18 years old, presenting to ED or AMU with acute respiratory illness (ARI)		
Planned Sample Size	200 patients		
Planned Study Period	Recruitment period: Up to three years from data of ethical approval (10 th January 2025 - 10 th January 2028)		
	Objectives	Outcome Measures	
Кеу	To evaluate the diagnostic accuracy of 3 host response tests for bacterial and viral infection compared to the reference standard of clinical adjudication	Positive percentage agreement (PPA) negative percentage agreement (NPA), Positive Predictive Value (PPV), Negative Predictive Value (NPV), Overall accuracy, AUROC (all with 95% confidence intervals).	
Exploratory	To evaluate the equivalence of EDTA blood and PAXgene RNA blood on gene expression values for Cepheid HR test (in development)	Correlation, Spearman's Coefficient, Kappa statistic	

5 Funding and resources

FUNDERS	FINANCIAL AND NON-FINANCIAL SUPPORT
NIHR CRN	Clinical fellow (1.0 WTE for 6 months)
BRC MII theme (via CRF)	Research nurse and Laboratory technician for
	sample processing
[name] PI fund	For consumables (Paxgene blood tubes)

6 Role of trial sponsor

The Sponsor is University Hospital Southampton NHS Foundation Trust (UHS), which is the organisation that is taking legal responsibility for the trial.

7 Background

Patients presenting to emergency departments are frequently given antibiotics that they do not need

Around 80-90% of adults presenting to emergency departments (ED) with acute respiratory infection (ARI) are treated with antibiotics (1,2), however much of this is unnecessary as around half of episodes of ARI are caused by viruses (3,4). This unnecessary antibiotic use is directly harmful to patients, as 20% of patients experience adverse events including C.difficile infection (5), and also promotes the development of antimicrobial resistance (AMR). AMR is one of the most serious threats to human health and measures to combat it are a global priority (6).

Testing for the presence of viruses in ARI does not reduce antibiotic use

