Reducing unnecessary antibiotic uses in ARI needs to be balanced against the risk of undertreating clinically important bacterial infection. Currently used single HR biomarkers (CRP and PCT) lack sufficient accuracy to do this (14). Tests with improved accuracy are therefore needed and must be implemented within a robust and safe testing strategy.

EDs are a priority area for antibiotic stewardships

As the interface between the community EDs are a priority area for antimicrobial stewardship (1) and the impact of antibiotic overuse use in EDs extends far beyond these departments as prescriptions started in ED are usually continued in other departments when patient are admitted, or in the outpatient setting if discharged (1). The use of point-of-care testing in the ED setting could be a critical component of a strategy to reduce AMR (31).

Review of existing evidence

A systematic literature review of published research and trial databases was undertaken using terms related to single and combined HR biomarker tests in terms of diagnostic accuracy, usability and clinical impact. For single biomarker accuracy (CRP and PCT) a recent meta-analysis demonstrated the following levels of accuracy for diagnosing bacterial infection in ARI; CRP (cut off of >50mg/L), sensitivity of 74.9%, specificity of 74.6%; PCT (cut off of >0.1ng/L) sensitivity of 73.6%, specificity of 74%, compared to clinical adjudication (14).

Other than FebriDx and MeMed BV no other combined HR-POCTs with CE marking were found. Excluding studies related only to COVID-19, 5 diagnostic accuracy studies evaluating FebriDx and 6 evaluating MeMed BV were found with 1 recent systematic review and meta-analysis (33) that included all of these studies. 1 NICE MedTech briefing was found that evaluated FebriDx (34). Overall, these studies suggest that both FebriDx and MeMed BV may have improved diagnostic accuracy for diagnosing bacterial infection (~85-95% for both sensitivity and specificity) compared to single biomarker tests. However, all these studies were company sponsored or supported and were assessed as being at high risk of bias, plus estimates of accuracy were imprecise due to small numbers of patient in individual studies. Therefore, the level of certainty of evidence is considered low (33).

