9.1 Sample size calculation

Assuming a sensitivity and specificity for the detection of bacterial infection (i.e. bacterial versus non-bacterial aetiology) of ~90%, for the combined HR-POCTs (33), a sample size of 200 samples containing 100 with bacterial (including bacterial/viral co-infection) and 100 patients with non-bacterial aetiology (i.e. viral and non-infected), using the reference standard of clinical adjudication, will allow an assessment of positive percentage agreement (sensitivity) and negative percentage agreement (specificity) with high precision (95%CIs of \pm 0) (39). In the PIs previous studies around 50% of all unselected patient with ARI have had bacterial infection as their adjudicated aetiology and therefore a sample of 200 patient should provide around 100 with bacterial infection. The samples size is based primarily on the performance of the bacterial component of the HR test as the principal intended use case of these tests is to guide antibiotic use.

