9.2 Statistical analysis plan

Test results from the combined HR-POCTs will be compared to adjudicated aetiology using the different adjudication methods. Positive percentage agreement (PPA, used in place of sensitivity to reflect an imperfect reference standard), Negative percentage agreement (NPA, used in place of specificity to reflect an imperfect reference standard), positive predictive value (PPV), negative predictive value (NPV), and overall accuracy (with 95% confidence intervals), will be calculated for both bacterial (vs non-bacterial) and viral (vs non-viral) infection. ROC curves will be generated and AUC with 95%CI calculated. Performance metrics including AUROC will be compared between the tests using Chi Squared test and DeLong test.

10 Data management

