10.6 Essential Document Retention & Archiving

Essential documents will include all signed protocols (and any amendments), copies of completed e-CRFs, signed ICFs from all subjects who consented, the Enrolment Log, the Screening Log, REC approvals and all related correspondence including approved documents and study correspondence.

The investigator and/or Sponsor must retain copies of the essential documents in the ISF for a minimum period following the end of the study. This is anticipated to be 15 years after completion of the study. Destruction of essential documents prior to this time will require authorisation from the Sponsor. The CI is responsible for, with the Sponsor, ensuring that documents are archived in accordance with local NHS R&D procedure at the close of the study. All essential documents will be stored securely in the CI's institution.

11 Monitoring

Based on the low risk of harm associated with the intervention in this non-CTIMP pilot study, no interim analysis, or Data Monitoring Committee is planned.

This study may be monitored and audited by University Hospital Southampton NHS Foundation Trust, under their remit as sponsor, and other regulatory bodies to ensure adherence to ICH GCP, UK Policy Framework for Health and Social Care Research, applicable contracts/agreements, and national regulations. All study related documents will be made available on request for monitoring and audit by UHS, the relevant REC or other licensing bodies.

12 Ethical and regulatory considerations

The investigators will ensure that this study is conducted according to the principles of the current revision of the Declaration of Helsinki and in conformity with the ICH GCP and local regulatory Indemnity

13 Further laboratory work on retained samples

The consent provided by participants expressly permits research (which may include validation of molecular and other test platforms for respiratory viruses, and pathogen sequencing as well as the measurement of host response biomarkers) on the stored samples, should any remain after this study has concluded. This work will primarily occur within the Clinical and Experimental Sciences (CES), Faculty of Medicine, University of Southampton, but collaboration with other institutions is possible at the discretion of the Chief Investigator.

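### The protocol calls the study fully powered, but N=200 is sized for the precision of each test alone and the claim is not supported for the planned between-test comparisons

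*Protocol*

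**What the plan says.** The title begins "Comparison of the performance of 3 Host Immune response tests". Under Study design and methods (section 7.1) the protocol states "We will conduct a fully powered diagnostic accuracy study" and, a paragraph later, "Measures of diagnostic accuracy will be calculated for each HR test separately and compared". Section 9.2 names the methods: "Performance metrics including AUROC will be compared between the tests using Chi Squared test and DeLong test".

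Section 9.1 starts from one accuracy value shared by the combined tests, "Assuming a sensitivity and specificity for the detection of bacterial infection (i.e. bacterial versus non-bacterial aetiology) of ~90" per cent. It justifies 100 bacterial plus 100 non-bacterial patients by the width of the 95% confidence intervals for positive and negative percentage agreement (PPA, NPA). It adds "The samples size is based primarily on the performance of the bacterial component of the HR test". It gives no between-test difference, power, significance level for comparisons, or expected discordance between tests.

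The stated aim (section 7.1) and the key objective in the synopsis are the accuracy of the tests against clinical adjudication. Section 11 (Monitoring) refers to the "intervention in this non-CTIMP pilot study". The evidence review in section 7 says that FebriDx and MeMed BV "may have improved diagnostic accuracy for diagnosing bacterial infection (~85-95% for both sensitivity and specificity").

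**The concern.** Power belongs to a hypothesis test against a stated alternative. The only hypothesis tests in the protocol's accuracy analysis are the between-test comparisons, and section 9.1 does not size the study for them. A reader who takes the title, the full-power claim and section 9.2 together will apply the claim to those comparisons. A non-significant result could then be taken to show that the tests perform alike, in a study meant to give independent evidence on tests that guide antibiotic use. Separately, one protocol should not describe the same study as both fully powered and a pilot.

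**Working it through.** **Inputs from the protocol.** Assumed accuracy is 90%, with 100 patients per reference class and about 50% bacterial prevalence (section 9.1). Published accuracy is about 85–95% (section 7). Samples for the tests are taken from all participants (section 7.3), so the data are paired.

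**Assumptions, because the protocol gives none for the comparison.** Two-sided 5% level; within-patient correlation φ between the two tests' results of 0, 0.3 or 0.5; pairs of true values chosen within 85–95%.

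**1. The plan's own basis.** 100 / 0.50 = 200, so the total fits the stated prevalence. The Wald half-width at 90% is 1.96 × √(0.90 × 0.10 / 100) = 0.0588, or ±5.9 points. The Wilson interval is 82.6–94.5% and Clopper-Pearson 82.4–95.1%. A ±6-point target needs 1.96² × 0.09 / 0.06² = 96.04, so 97 per class. N=200 is therefore consistent with a precision target of about ±6 points. The half-width printed in section 9.1 is not legible in the text available, so it cannot be checked directly.

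**2. Power to compare PPA (or NPA) between two tests, n=100.** For true values p1 > p2:
- both correct: p11 = p1·p2 + φ·√(p1(1−p1)·p2(1−p2))
- discordant: p01 = p2 − p11, and p10 = p01 + (p1 − p2)
- power = the sum over d of P(d discordant pairs out of 100) × P(|2b − d|/√d > 1.96), with b ~ Binomial(d, p10/(p10+p01)).

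Example, 90% v 85% at φ=0.3: p11 = 0.765 + 0.3 × √(0.09 × 0.1275) = 0.7971; p01 = 0.0529; p10 = 0.1029; power 24%.

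| True values | φ | p10 | p01 | McNemar, asymptotic | McNemar, exact |
|---|---|---|---|---|---|
| 90 v 85 | 0 | 0.1350 | 0.0850 | 19% | 13% |
| 90 v 85 | 0.3 | 0.1029 | 0.0529 | 24% | 17% |
| 90 v 85 | 0.5 | 0.0814 | 0.0314 | 30% | 22% |
| 95 v 90 | 0 | 0.0950 | 0.0450 | 26% | 19% |
| 95 v 90 | 0.3 | 0.0754 | 0.0254 | 33% | 24% |
| 95 v 90 | 0.5 | 0.0623 | 0.0123 | 45% | 30% |
| 95 v 85 | 0 | 0.1425 | 0.0425 | 67% | 58% |
| 95 v 85 | 0.3 | 0.1192 | 0.0192 | 81% | 74% |
| 95 v 85 | 0.5 | 0.1036 | 0.0036 | 95% | 90% |

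A chi-squared calculation that treats the two tests' results as independent samples of 100 gives 19%, 27% and 66% for the three pairs. If the errors were fully nested (p01 = 0), power for a 5-point difference would be 74% asymptotic and 38% exact, still below 80%. At 0.05/3, to allow for three pairwise comparisons, 95 v 85 gives 48%, 65% and 87% at φ = 0, 0.3 and 0.5.

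**3. Smallest difference with 80% power** (asymptotic, unadjusted, φ = 0 / 0.3 / 0.5): 15 / 12 / 10 points below 90%, and 12 / 10 / 8 points below 95%.

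**4. Patients needed for 80% power at 5 points.** n = (1.96√pd + 0.84√(pd − δ²))² / δ², with pd = p10 + p01 and δ = 0.05. For φ 0.5 down to 0, this gives 232–438 per class for 95 v 90 (464–876 in total at 50% prevalence) and 353–689 per class for 90 v 85 (706–1,378 in total).

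**5. AUROC.** With Hanley-McNeil variances, 100 per class and assumed correlation 0–0.5 between the two AUROCs, power is 29–50% for 0.90 v 0.85, 44–70% for 0.95 v 0.90 and 88–99% for 0.95 v 0.85.

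**The case against.** The strongest reply is that the sentence claims full power for a diagnostic accuracy study, not for a comparison. The aim and key objective are accuracy against adjudication, the key outcomes are accuracy measures with 95% confidence intervals, and section 9.1 sizes exactly that. On this view the word is loose usage for adequately sized, and the comparison is a secondary analysis. This largely stands: N=200 fits the stated objective, and nothing here shows that the sample is too small for it. What remains is that the title, section 7.1 and section 9.2 all announce comparisons to which the claim will be applied, and that section 11 contradicts it.

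Three stronger readings are tempting and should be resisted.
- *The study cannot detect any plausible difference.* The figures do not show this. At the full width of the cited range (95 v 85), asymptotic power is 67–95%, and for AUROC 88–99%. The shortfall is clear near 5 points and depends on the correlation near 10.
- *Differences above 10 points are ruled out.* The protocol itself rates the evidence for the 85–95% range as of low certainty. That range covers FebriDx and MeMed BV; for Triverity the text reports only similar levels.
- *The protocol intends to declare the tests equal.* It does not. Equivalence is mentioned only for EDTA against PAXgene blood. The risk lies in how a non-significant result might be read.

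**Conclusion.** The concern holds in a limited form. The sample size is a precision size of about ±6 points per test and suits the per-test objective. The claim of full power has no support for the between-test comparisons and conflicts with the pilot label. Power for a 5-point difference is 19–30% from 90% and 26–45% from 95%. For 95 v 85 it is 67–95%, reaching 80% only at φ of about 0.3 or more. These figures rest on assumed true values, a two-sided 5% level, asymptotic McNemar, 100 patients per class, φ of 0–0.5 and no multiplicity adjustment. The exact test or an adjustment lowers them.

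**What to change.** - **Study design and methods (section 7.1):** replace the full-power wording with a statement that the study is sized to estimate each test's bacterial PPA and NPA to about ±6 percentage points. Reconcile this with the pilot label in section 11.
- **Sections 9.1 and 9.2:** describe between-test comparisons as secondary estimation, reported as paired differences with 95% confidence intervals. Use McNemar-type paired methods for PPA and NPA instead of an unpaired chi-squared test, and the paired form of DeLong for AUROC. State that non-significance is not evidence of equal performance.
- **If a detectable difference is quoted, give its assumptions:** about 10–15 points from a 90% baseline or 8–12 points from 95%, for 80% power, asymptotic McNemar, φ of 0–0.5, unadjusted for three pairwise comparisons.

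The cost is a few sentences and a more modest claim. No extra patients or samples are needed, and N stays at 200.

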7.2 Participant eligibility criteria

Inclusion criteria

- Is a patient in the ED or AMU, Southampton General Hospital, UHS
- Aged ≥ 18 years old
- Able to be recruited and sampled within 24 hours of arrival in the ED or AMU
- Has the capacity to consent to the study
- Has at least one of the following acute respiratory symptoms*:
 - Cough
 - o Shortness of breath
 - o Coryza
 - Sore throat
 - o Wheeze
 - o Fever (where not definitively explained by another cause)
 - o Reported exacerbation of a chronic respiratory condition (e.g., asthma, COPD)

We note that patients will have been seen and assessed by a triage nurse or other triaging clinician before being approached to enrol in the trial. However, patients may not have been seen by their treating clinician before being approached to enrol in the trial.

Exclusion criteria

- Not fulfilling all inclusion criteria
- Declines nasal/pharyngeal swabbing, finger prick testing or venesection
- Underlying severe bronchiectasis, cystic fibrosis, severe immune suppression

Patient-participant screening and consent

Participant Identification & Screening

Patients in the ED or AMU who have been seen and assessed by the triage nurse or another clinician may be approached for consideration of enrolment into the trial. Staff in the ED may highlight patients for consideration to the research team. Review of electronic systems and triage notes may assist the research team's identification and assessment of eligibility for potential participants. The research team comprises primarily of doctors and nurses who are familiar with, and often work in, the ED environment. The research team have an established relationship of doing trials in the ED and are integrated into acute clinical care.

Potential participant notes will be compared to inclusion and exclusion criteria to ensure likely eligibility before approaching the patient.

Consent

Discussion of the study will be undertaken with the patient by a research team member and a generic SRB Participant Information Sheet (PIS) provided to the patient. There will be opportunity for the participant to ask questions. Research staff will ensure that only participants that meet all the inclusion criteria and none of the exclusion criteria are enrolled and randomised in the study.

If the patient is willing to participate in the study and fulfils the eligibility criteria, the research team will obtain written informed consent using the generic SRB Informed Consent Form (ICF). In view of

^{*}Acute respiratory symptoms are defined as new symptoms or chronic symptoms with an acute worsening of less than or equal to seven days duration.

the need for the rapid return of test results to facilitate onward patient care the usual 24-hour consideration period for a participant cannot apply in this study. Given the low-risk nature of sample collection and the brevity of the patient's physical involvement with the study, the research team feels that a shorter time to consider involvement is reasonable.

If the patient is willing to be involved in the study and is able to sign and date the ICF to indicate consent, they will do so. If the patient can provide informed consent but has difficulty writing or otherwise filling in the ICF, informed consent from the patient will be verified by an independent witness (this may be a staff member not associated with the study, or friend or relative of the patient), and the independent witness would then fill in, sign and date the ICF on the patient's behalf. Both the person taking consent and either the patient or independent witness must personally sign and date the ICF. A similar process can be used for patients with an understanding of English that may be insufficient to read and take in the participant information sheet and consent form information, but who retains the capacity to make decisions for themselves. In this instance, the patient must fill in the consent form, but the witness must also sign that they have assisted the person in fully understanding the consent process. Copies of the ICF will be given to the patient (and witness if applicable) and put into the patient's notes. The original ICF is stored securely by the study team.

Each patient will be assumed to have capacity unless it is established that they lack capacity. As this study may not offer any direct benefit to the participants, patients lacking capacity and unable to consent for themselves will not be eligible for this study.

